² Blood pressure and pulse rate should be measured after the patient has been in a supine or sitting position for 5 minutes. Blood pressure should be assessed on the same arm throughout the study. Physical examinations will be performed on the scheduled day, even if study treatment is being interrupted.

³ BSA will be calculated to verify that $BSA > 1.2 \text{ m}^2$ to ensure that an individual patient's selinexor dose would not exceed 70 mg/m^2 twice weekly. If the patient's weight fluctuates substantially, BSA should be re-calculated at each treatment visit. BSA should be re-calculated prior to any selinexor/placebo dose change.

⁴ The following assessments may be performed if clinically indicated during the study: ECGs, urinalysis, hematology, complete or limited serum chemistry, coagulation tests, pregnancy testing, and nutritional consultation. Clinical laboratory tests will be collected and analyzed on the scheduled day, even if study treatment is being interrupted (see Section 10.6.2.1).

⁵ ECGs on Day 1 of Cycles 1 and 2 during blinded study treatment are to be performed just prior to the blood sample taken 2 hours postdose (approximately at the expected t_{max} of plasma selinexor).

⁶ For females of childbearing potential only; must have a negative serum hCG pregnancy test at Screening within 3 days before the first dose of blinded study treatment. Test sensitivity for hCG must be $\geq 25 \text{ mIU/mL}$.

⁷ A tumor biopsy will be collected during Screening in order to perform confirmatory histology at a central laboratory (results not required for randomization and initiation of treatment) unless appropriate archival material (ie, of DDLS tissue) is available (see Section 10.4). If sufficient material is available from the pretreatment (screening) biopsy sample (archival or fresh), a portion of the sample will be used for **CC1** testing and one additional tumor biopsy will be collected at either Cycle 1 Day 22 or Cycle 2 Day 1 for **CC2** to assess treatment-related changes using immunohistochemical, genomic, and/or proteomic assays (see Section 10.11.3). Biopsies are required if feasible. The feasibility of the biopsy procedure, in terms of patient safety and tumor accessibility, will be determined by the Investigator. Note: This second biopsy (eg, either Cycle 1 Day 22 or Cycle 2 Day 1) should not be collected from adolescent/pediatric patients for exploratory studies if there appears to be a potential for serious risk for the patient.

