²³ For female patients of childbearing potential only; pregnancy testing (serum hCG or high sensitivity urine) is required prior to dosing on Day 1 of Cycles ≥ 2 and at the EoBT Visit or within 3 days before the first dose of open-label selinexor (serum hCG). A positive urine pregnancy test will be confirmed by a serum pregnancy test. Test sensitivity for hCG must be ≥ 25 mIU/mL.

Table 2: Schedule of Assessments and Study Activities: Open-Label Selinexor

- EoBT Visit serves as baseline of Open-Label Selinexor; The EoBT Visit may occur at open-label (OL)-C1 D1 visit but must be \leq 14 days of last blinded dose. OL C1 D1 must occur within 14 days of the EoBT Visit.
- Patients in the selinexor arm who continue selinexor but as open-label treatment must complete the EoBT Visit before their next scheduled selinexor dose to maintain continuity of selinexor dosing from blinded to open-label treatment.
- Physical examination assessments and laboratory assessments done at the EoBT Visit do not need to be repeated at OL-C1 D1.

| | Open-Label Cycle 1 (42 days/6 wks) per cycle) | | Open-Label Cycle 2 | | Open-Label Cycle \geq 3 | End of Treatment (EoT) Visit | Safety Follow- up Call ¹⁵ | Survival Follow-up ¹⁶ |
|---|--|-----------------------------|-----------------------|-------------------------------------|------------------------------|------------------------------------|---|-------------------------------------|
| Schedule of Visit | Days 1, 8*, 15*, 22, 29* and 36* | Day 3 only ¹⁷ | Days 1, 15 and 29* | Days 10, 24 and 38 ¹⁷ | Days 1 and 22 | \leq 14 days Post- Last Dose | 30 days after last dose | Every 3 months |
| Visit window [±days] | ±1 day | + 1 day | ± 2 days | + 1 day | ± 2 days | | +7 days | ±14 days |
| Visit number | OL1-6 | Phone | OL7-9 | Phone | OL \geq 10 | In Office | Phone | Phone |
| Open-label informed consent ¹ | X (if not obtained at EoBT Visit) | | | | | | | |
| Clinical Assessments (if performed at EoBT, do not repeat at C1 D1) | | | | | | | | |
| Physical examination and vital signs (blood pressure, pulse, temperature) ² | X | | X | | X | X | | |
| Weight (indoor clothing without shoes) | X | | X | | X | X | | |
| Height (without shoes) | | | X (D1 only) | | X (D1 only) | X | | |
| BSA ³ | | | X (D1 only) | | X (D1 only) | X | | |
| ECOG | X (D1 only) | | X (D1 only) | | X (D1 only) | X | | |
| 12-lead ECG ⁴ | X (D1 only) | | | | | X | | |

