| | Open-Label Cycle 1 (42 days/6 wks) per cycle) | | Open-Label Cycle 2 | | Open-Label Cycle ≥ 3 | End of Treatment (EoT) Visit | Safety Follow- up Call ¹⁵ | Survival Follow-up ¹⁶ |
|---|--|-----------------------------|---|-------------------------------------|---|--|---|-------------------------------------|
| Schedule of Visit | Days 1, 8*, 15*, 22, 29* and 36* | Day 3 only ¹⁷ | Days 1, 15 and 29* | Days 10, 24 and 38 ¹⁷ | Days 1 and 22 | ≤ 14 days Post- Last Dose | 30 days after last dose | Every 3 months |
| Visit window [±days] | ±1 day | + 1 day | ± 2 days | + 1 day | ± 2 days | | +7 days | ±14 days |
| Visit number | OL1-6 | Phone | OL7-9 | Phone | OL ≥ 10 | In Office | Phone | Phone |
| Laboratory Assessments (if performed at EoBT, do not repeat at C1 D1) | | | | | | | | |
| Urinalysis ⁴ | X (D1 only) | | X (D1 only) | | X (D1 only) | X | | |
| Hematology ⁴ | X (D1 only) | | X (D1 only) | | X (D1 only) | X | | |
| Complete serum chemistry ⁴ | X (D1 only) | | X (D1 only) | | X (D1 only) | X | | |
| Limited serum chemistry ⁴ | X (D8, D15, D22, D29, D36) | | X (D15, D29) | | X (D22 only) | | | |
| Coagulation tests ⁴ | X (D1 only) | | X (D1 only) | | X (D1 only) | X | | |
| Pregnancy test ^{4, 5, 18} | | | X (D1 only) | | X (D1 only) | X | | |
| Tumor biopsy ⁶ (Only patients who cross over from placebo) | X (C1 D22 only; or may be taken on C2 D1) | | X (C2 D1 only; if not taken on C1 D22) | | | | | |
| Imaging | | | | | | | | |
| CT (preferred) or MRI scan for tumor measurement ⁷ | | | X (D1 only) | | X (D1 of every odd # cycle) | X (if ≥ 4 weeks since last prior scan AND required to document disease or clinical progression) | | |
| Assessment of progression/ extent of liposarcoma following each tumor scan (RECIST v. 1.1) ⁸ | | | X (D1 only) | | X (when tumor scans are performed) | X (If tumor scan is performed) | | |

| | Open-Label Cycle 1 (42 days/6 wks) per cycle) | | Open-Label Cycle 2 | | Open-Label Cycle ≥ 3 | End of Treatment (EoT) Visit | Safety Follow- up Call ¹⁵ | Survival Follow-up ¹⁶ |
|---|---|-----------------------------|-----------------------------------|-------------------------------------|------------------------------|------------------------------------|---|-------------------------------------|
| Schedule of Visit | Days 1, 8 ² , 15 ² , 22, 29 ² and 36 ² | Day 3 only ¹⁷ | Days 1, 15 and 29 ² | Days 10, 24 and 38 ¹⁷ | Days 1 and 22 | ≤ 14 days Post- Last Dose | 30 days after last dose | Every 3 months |

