⁵ Females of childbearing potential who are proceeding to open-label selinexor must have a negative serum hCG pregnancy test at the EoBT Visit (or within 3 days before the first dose of open-label selinexor). Test sensitivity for hCG must be ≥ 25 mIU/mL.

⁶ Tumor biopsy to be taken only from patients who cross over from blinded placebo to open-label selinexor. If a biopsy sample was obtained during blinded treatment (pre- or post-dosing) within 12 months prior to the first dose of open-label selinexor, one additional biopsy will be taken at either Cycle 1 Day 22 OR Cycle 2 Day 1 for **CCI**. Portions of this biopsy will be formalin-fixed and frozen-unfixed as described in the *Laboratory Manual*. Biopsies are required if feasible. The feasibility of the biopsy procedure, in terms of patient safety and tumor accessibility, will be determined by the Investigator. This second biopsy (eg, either Cycle 1 Day 22 or Cycle 2 Day 1) should not be collected from adolescent/pediatric patients for exploratory studies if there appear to be a potential for serious risks for the patient. Patients in the selinexor arm who continue on selinexor but as open-label treatment are not required to have an additional tumor biopsy on Cycle 1 Day 22 or Cycle 2 Day 1 of open-label treatment.

⁷ CT (or MRI if CT contraindicated) scans will be performed approximately 6 and 12 weeks after the first dose of open-label selinexor (ie, Day 1 of Cycles 2 and 3), then every 12 weeks (ie, Day 1 of odd-numbered Cycles ≥ 5) thereafter until PD to assess tumor size (one, two and three dimensions) and evaluate site of disease and distant sites (abdomen, pelvis, chest). For a given patient, the same imaging modality should be maintained throughout the study. Copies of scan data will be provided to the central reader for two-dimensional and three-dimensional measurements for determination of tumor responses (see *Imaging Manual* for details).

⁸ Assessment of liposarcoma per RECIST v. 1.1 ([Eisenhauer 2009; Appendix 2](#)) by the central reader.

CCI

¹¹ For patients in the placebo arm who cross over to open-label selinexor, the nutritional consultation should occur on C1 D1 before the first dose of open-label selinexor. The nutritional consultation is not required at C1 D1 of open-label selinexor treatment for patients in the selinexor arm who continue on selinexor but as open-label treatment. See Section [10.7.3](#).

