9.2. Description of Study Days: Open-label Selinexor

Please note:

- EoBT Visit serves as baseline of Open-Label Selinexor; The EoBT Visit may occur on the day of the patient's first open-label dose (OL-C1 D1 Visit) but must be ≤ 14 days of last blinded dose. OL C1 D1 must occur within 14 days of the EoBT Visit.
- Patients in the selinexor arm who continue selinexor but as open-label treatment must complete the EoBT Visit before their next scheduled selinexor dose to maintain continuity of selinexor dosing from blinded to open-label treatment.
- Physical examination assessments and laboratory assessments done at the EoBT Visit do not need to be repeated at OL C1 D1.

9.2.1. Visits OL1-6 (Cycle 1: Days 1, 8*, 15*, 22, 29*, and 36* [± 1 days]); Return to the Clinic

There are six clinic visits (ie, Days 1, 8*, 15*, 22, 29*, and 36*) during the first six-week cycle (Cycle 1).

Visits (ie, Days 8, 15*, 29*, and 36*) are not required for patients who continue selinexor but as open-label treatment.

The following study assessments will be performed during Cycle 1, as specified in [Table 2](#).

- Physical examination and vital signs (blood pressure, pulse, and body temperature) (Days 8*, 15*, 22, 29*, and 36*) [Section 10.6.1.1](#)
- Weight (Days 8*, 15*, 22, 29*, and 36*) ([Section 10.6.1.2](#))
- Limited serum chemistry (Days 8*, 15*, 22, 29* and 36*) ([Section 10.6.2.1](#))
- Tumor biopsy, only for patients who cross over from blinded placebo to open-label selinexor and have sufficient material available from a biopsy sample obtained during blinded study treatment (pre- or post-dosing) within 12 months prior to the first dose of open-label selinexor (Day 22 only). Note: If the biopsy is not performed on Cycle 1 Day 22, it may be performed on Cycle 2 Day 1 (see [Section 9.2.2](#)). Patients in the selinexor arm who continue on selinexor but as open-label treatment are not required to have an additional tumor biopsy on Cycle 1 Day 22 of open-label treatment. See [Section 10.11.3](#) for biopsy details.
- CCI
- CCI
- Nutritional consultation (should occur on Day 1 before the first dose of open-label selinexor) for patients in the placebo arm who cross over to open-label selinexor. The nutritional consultation is not required at C1 D1 of open-label selinexor treatment for patients in the selinexor arm who continue on selinexor but as open-label treatment. See [Section 10.7.3](#).
- Selinexor: in clinic dosing and dispensing of for home use

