10.6.2.2. Pregnancy Testing

Pregnancy testing will be performed for females of childbearing potential only. A negative serum hCG pregnancy test must be obtained at Screening within 3 days before the first dose of blinded study treatment. For females of childbearing potential who are proceeding to open-label selinexor a negative serum hCG pregnancy test must be obtained at the EoBT Visit (or within 3 days before the first dose of open-label selinexor). Test sensitivity for hCG must be ≥ 25 mIU/mL.

Pregnancy testing (serum hCG or high sensitivity urine) is also required for females of childbearing potential prior to dosing on Day 1 of Cycles ≥ 2 during both blinded and open-label treatment and at the EoT Visit (serum hCG). A positive urine pregnancy test will be confirmed by a serum pregnancy test.

Pregnancy testing may be performed if clinically indicated during the study.

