12.1.3. Dosing Information

Selinexor tablets should be taken orally with at least 120 mL (4 ounces) of water. Selinexor can be taken with or without food. For additional details on drug formulation, preparation, and administration, please refer to the *Pharmacy Manual* and the selinexor IB.

In order to avoid contact with skin, tablets must be swallowed whole and should not be crushed.

Blinded Study Treatment (Phases 2 and 3):

Selinexor and matching placebo will be administered as fixed blinded oral doses of three 20 mg tablets given twice weekly (eg, Day 1 Monday and Day 3 Wednesday or Day 1 Tuesday and Day 3 Thursday or Day 1 Wednesday and Day 3 Friday) on Weeks 1-6 of each 6-week (42-day) cycle until PD, intolerance, consent withdrawal, or unblinding. Patients with a BSA < 1.2 m² as calculated per [Dubois 1916](#) or [Mosteller 1987](#) will be excluded from the study. Selinexor will be administered as a flat-fixed dose, and not by body weight or BSA.

Open-Label Selinexor:

Patients on open-label selinexor will receive selinexor 60 mg twice-weekly during Weeks 1-6 of each 6-week (42-day) cycle.

The following 4 groups of patients may receive open-label selinexor:

- (a) Patients in the placebo arm who have PD per RECIST v. 1.1 during blinded study treatment who elect to cross over to open-label selinexor

- (b) Patients in the selinexor arm who have PD per RECIST v. 1.1 during blinded study treatment who may derive benefit from continued treatment with selinexor (see Section 7.2.4).
- (c) Patients in the placebo arm who are receiving blinded study treatment at the time of the primary PFS analysis at the end of Phase 3 who elect to continue to cross over to open-label selinexor
- (d) Patients in the selinexor arm who are receiving blinded study treatment at the time of the primary PFS analysis at the end of Phase 3 who elect to continue selinexor but as open-label treatment

C1D1 of treatment with open-label selinexor for all 4 groups of patients listed above must occur within 14 days of the patient's EoBT Visit. For patients in the selinexor arm during blinded study treatment who continue selinexor but as open-label treatment there will be no break in the patient's twice-weekly dosing schedule. These patients must complete the EoBT Visit before their next scheduled selinexor dose to maintain continuity of selinexor dosing from blinded to open-label treatment.

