13.3. Procedures for Handling Special Situations

13.3.1. Pregnancy and Breastfeeding

Note: Pregnancy per se is not considered to be an AE; however, it is discussed here because of the importance of reporting pregnancies that occur during studies and because a medical occurrence observed in the mother or fetus/newborn would be classified as an AE.

During both blinded and open-label treatment, female patients of childbearing potential and fertile male patients will be informed as to the potential risk of conception while participating in this study and will be advised that they must use highly effective contraception listed below (ie, results in a low failure rate when used consistently and correctly) during the dosing period and for a period of at least 3 months after the end of treatment.

Highly effective methods include:

- combined (estrogen and progestogen containing) hormonal contraception associated with inhibition of ovulation:
 - oral
 - intravaginal
 - transdermal
- progestogen-only hormonal contraception associated with inhibition of ovulation:

- oral
- injectable
- implantable
- intrauterine device
- intrauterine hormone-releasing system
- bilateral tubal occlusion
- vasectomized partner
- sexual abstinence

During both blinded and open-label treatment a pregnancy test will be performed on each premenopausal female patient of childbearing potential prior to the first dose of study drug, on Day 1 of Cycles ≥ 2 while on treatment, and again at treatment discontinuation during the End-of-Treatment visit. A negative pregnancy test must be documented prior to administration of study drug.

If a patient is confirmed pregnant during the study, study drug administration must be discontinued immediately. The Investigator must immediately notify the sponsor medical monitor of this event and record the Pregnancy on the Pregnancy Form. The initial information regarding a pregnancy must be forwarded to Karyopharm Pharmacovigilance by email or fax within 24 hours of first knowledge of its occurrence. A pregnancy report form is provided by Karyopharm.

The pregnancy should be followed up to determine outcome, including spontaneous or voluntary termination, details of the birth, and the presence or absence of any birth defects, congenital abnormalities, or maternal and/or newborn complications.

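### At crossover from placebo, a pregnancy test up to 14 days old is accepted before the first selinexor dose (3 days at blinded start), and the hCG sensitivity limit, read literally, is reversed

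*Protocol*

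**What the plan says.** **Blinded start.** Table 1 footnote 6 of the Protocol says a woman of childbearing potential "must have a negative serum hCG pregnancy test at Screening within 3 days before the first dose of blinded study treatment". Section 10.6.2.2 gives the same rule.

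**Open-label start.** Section 10.6.2.2 says "a negative serum hCG pregnancy test must be obtained at the EoBT Visit (or within 3 days before the first dose of open-label selinexor". Table 2 footnote 5 and sections 9.1.6 and 12.2.5.3 carry the same pair of options. Table 1 footnote 23 writes them without the parenthesis, as a plain either/or: "at the EoBT Visit or within 3 days before the first dose of open-label selinexor (serum hCG".

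**Gap between EoBT and the first open-label dose (OL C1D1).** Section 9.2 and the notes above Table 2 say "OL C1 D1 must occur within 14 days of the EoBT Visit". Section 12.1.3 applies the same limit to every route into open-label treatment: "for all 4 groups of patients listed above must occur within 14 days of the" EoBT Visit. The EoBT Visit may also be held on the day of the first open-label dose.

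**Repeat testing at OL C1D1.** The pregnancy-test row of Table 2 is blank in Cycle 1 and first marked at Cycle 2 Day 1. The laboratory header above that row says "if performed at EoBT, do not repeat at C1 D1". The section 9.2.1 list for the first open-label visit names several laboratory tests but no pregnancy test. Section 13.3.1 adds a general rule: "A negative pregnancy test must be documented prior to administration of study drug".

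**Assay limit.** Table 1 footnotes 6 and 23, Table 2 footnotes 5 and 18, and section 10.6.2.2 each ask for an hCG test sensitivity at or above 25 mIU/mL.

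**Partner pregnancies.** Section 13.3.1 requires every partner pregnancy to be reported within 24 hours, but limits follow-up to partners of men on a regimen that contains selinexor. Section 7.8 keeps assignment from patients, families and the study team until unblinding is allowed.

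**The concern.** A placebo patient who crosses over has had no selinexor, so OL C1D1 is her first exposure, just as Cycle 1 Day 1 is for a patient randomized to selinexor. In Phase 3 a woman starting blinded treatment has a two-in-three chance of receiving selinexor; at crossover exposure is certain. The protocol nevertheless sets the looser limit on test age at crossover and gives no reason. Section 12.2.5.3 itself warns that the study treatments may harm a fetus.

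The rule governs crossover at progression (section 7.2.1) and crossover of placebo patients still on blinded treatment at the primary PFS analysis (section 7.2.3).

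The assay wording matters because pregnancy tests, like the other laboratory work, are run locally. A site that follows the text literally could accept a less sensitive test and reject a better one.

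**Working it through.** No sample-size or alpha calculation is involved. The check is visit-window arithmetic and a reading of the rules side by side.

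**1. Maximum age of the test at first selinexor exposure**

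| Setting | Governing rule | Maximum age |
|---|---|---|
| Blinded start | Serum test within 3 days before dose (Table 1 footnote 6; 10.6.2.2) | 3 days |
| Placebo crossover, test at EoBT | EoBT test accepted (10.6.2.2 and four other places); OL C1D1 within 14 days of EoBT (9.2, notes above Table 2, 12.1.3) | 14 days |
| Placebo crossover, other option | Serum test within 3 days before dose | 3 days |

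If the test is done at EoBT on day X, OL C1D1 may be any day from X to X + 14, so the test is 0 to 14 days old. The 3-day option is an alternative and does not cap the EoBT option. Difference between the maxima: 14 − 3 = 11 days. With a 3-day rule at crossover it becomes 3 − 3 = 0.

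**2. Does another rule close the gap?**

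- Table 2 schedules no Cycle 1 pregnancy test, and the no-repeat instruction heads the block of rows that contains it. Section 9.2 and the notes above Table 2 also waive repeats of EoBT laboratory work.
- The section 9.2.1 first-visit list omits the test.
- Section 13.3.1 requires a documented negative result before dosing but sets no limit on its age.

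None of these limits the age of an EoBT test.

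**3. Who is affected?** Women of childbearing potential crossing over from placebo whose EoBT test is more than 3 days before OL C1D1. Selinexor-arm patients who continue are already exposed and must complete EoBT before their next scheduled dose (section 9.2), so they are not part of this point.

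A ceiling on scale: SAP section 1.1 reports 285 Phase 3 patients randomized 2:1, so about 285 / 3 = 95 on placebo; the Protocol synopsis gives 30 on placebo in Phase 2. That makes about 95 + 30 = 125 patients of both sexes, of whom only the subset just described is affected. The documents do not give the share of childbearing potential, so no closer figure is possible.

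**4. Direction of the hCG limit.** Sensitivity stated as a concentration is the lowest level the test detects, so a smaller number means a more sensitive test. At or above 25 mIU/mL admits detection limits of 25, 50 or 100 and excludes any below 25. At or below 25 does the opposite.

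**5. Partner follow-up.** Applying the section 13.3.1 condition requires knowing the man's arm. After centrally determined progression, the patient and investigator know it (section 11.3.1). Before that, and for men who stop without progression until the primary PFS analysis (section 7.2.2), they normally do not, so the condition cannot be applied.

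**The case against.** The strongest reply is that a crossover patient differs from one at screening. She has agreed to highly effective contraception and, from Cycle 2, has been tested before dosing on Day 1 of each blinded cycle. Scans that show progression are scheduled on Day 1 visits, so a Day 1 test will often precede crossover, with the serum test at EoBT in addition. On treatment the protocol tests once per 42-day cycle and so accepts dosing on a test about 42 days old; 14 days is well inside that. The parenthesis may also have been meant to require a retest when EoBT is more than 3 days before dosing.

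Much of this stands as a reason to expect few affected patients. It does not close the gap. The 42-day interval is surveillance of patients already on treatment; the like-for-like comparison is first exposure with first exposure, for which the protocol chose 3 days. Crossover at the primary PFS analysis is not tied to a Day 1 visit. The retest reading is possible, but the text does not say it, and the plain either/or in Table 1 footnote 23 points the other way.

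On the assay, the intended meaning was probably a test at least as sensitive as 25 mIU/mL, since section 10.6.2.2 also refers to high-sensitivity urine testing. That makes the correction editorial, but the threshold as written is still wrong.

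On partners, the conflict lasts only while assignment is unknown, and 24-hour reporting already applies to all. Both points stand and limit the remedy.

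**Conclusion.** The point holds and should be corrected. At first selinexor exposure the permitted test age is up to 14 days for placebo crossovers against 3 days at blinded start, a maximum excess of 11 days. This rests on reading the two timings as alternatives, as written. Few patients are likely to be affected, and no efficacy result changes. The hCG limit, read literally as a detection limit, is reversed in five places. The partner-pregnancy condition is minor.

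Four stronger readings are tempting but unsupported:

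- A reader might infer from the blank Cycle 1 cell in Table 2 that no test is required before open-label selinexor. That row cites footnote 5, under which the patient "must have a negative serum hCG pregnancy test at the EoBT Visit (or within 3 days before the first dose of open-label selinexor", and section 13.3.1 also requires a negative result. The gap is the age of the test, not its absence.
- A reader might take 14 days as typical. EoBT may fall on the day of the first open-label dose, so it is only a limit.
- A reader might add the 42-day cycle and compare 14 + 42 = 56 days with 3 + 42 = 45 days to the next scheduled test. Selinexor exposure before that test is 42 days either way; the difference is the same 11 days.
- A reader might infer that insensitive assays were used, or that partners of men known to have had only placebo need follow-up. The documents show neither.

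**What to change.** **(a) Timing.** For placebo patients crossing over, require a negative serum hCG test within 3 days before OL C1D1; an EoBT test counts only if it falls in that window. Amend Table 1 footnote 23, Table 2 footnote 5, and sections 9.1.6, 10.6.2.2 and 12.2.5.3. Add the test to the Cycle 1 cell of Table 2 and to the section 9.2.1 list. Exempt it from the no-repeat wording in the Table 2 laboratory header, the notes above Table 2, and section 9.2.

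**(b) Assay.** In Table 1 footnotes 6 and 23, Table 2 footnotes 5 and 18, and section 10.6.2.2, require a limit of detection of 25 mIU/mL or lower.

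**(c) Partners.** In section 13.3.1, follow every reported partner pregnancy, with the partner's consent, unless and until unblinding shows that the man received only placebo.

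The cost is wording at about a dozen places, at most one repeated or re-timed blood test for a few crossover patients, and a few more partner-consent requests.
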